Recruitment procedures. We are requesting approval to enrol/randomize up to 40 (20 treatment and 20 control) HIV infected women meeting the aforementioned inclusion criteria from PMMH Gateway clinic. Potential participants will be approached about study participation by a trained research assistant (experienced in sexual and reproductive health fieldwork) as

they wait in the clinic queue. Those who express interest will be invited to speak with the study research assistant to learn more about study participation and be screened for eligibility; written signed consent to screening will be obtained. Those who volunteer to participate will complete the informed consent process. These procedures will be completed in a private setting, and procedures will be undertaken to ensure women do not lose their place in line. This strategy has successfully been used for other studies at PMMH antenatal clinic. Phase I of this protocol was approved by HREC (Clearance Certificate M110963), which utilized the same procedures. The research assistant will use an eligibility screening script to track all screened potential participants. These data will be recorded for study data reports. Review of the inclusion/exclusion checklists will be part of regular supervisory meetings between the local site PI, project manager and the research assistant.

Intervention development. The preliminary intervention content is based on two established cognitive-behavioural interventions: problem-solving therapy (PST; ³⁹) and Cognitive Behavioural Therapy for Adherence and Depression (CBT-AD; ⁴⁰). PST was selected as it is an effective depression treatment in its own right,⁴¹ but because many of the challenges that HIV infected women in the perinatal period face (e.g., managing stigma, overcoming barriers to PMTCT adherence) are strong targets for a problem-solving intervention, and the group setting may contribute to a rich range of potential solutions to these problems. Furthermore, PST is straightforward to deliver, increasing the likelihood of successful delivery by a wider variety of individuals with varied training in psychosocial interventions. CBT-AD combines traditional cognitive-behavioural skills (including problem-solving) for depression with adherence counselling skills. The “Lifesteps” module of CBT-AD has been modified to reflect the adherence needs of HIV-infected women during the perinatal period. The intervention manual is included as an Appendix.

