The intervention has been conceptualized as a group intervention as it has been proposed that interventions that make use of and foster social support may be helpful in decreasing social isolation and stigma among individuals living with HIV ¹⁰. In addition, interventions that target social networks and strengthen group ties have also been used to empower marginalized groups, and to effect health related behaviour change related to HIV prevention (e.g., ⁴²⁻⁴⁴). Lastly, group mental health interventions are cost-effective, which is of particular benefit in resource-limited settings ^{44,45}. The ideal number of participants per group will be approximately 2-10. In the event that enough participants cannot be recruited to participate in group-based sessions (i.e. due to scheduling concerns), individual sessions will be conducted. This data will be recorded and analysed as part of the feasibility and acceptability data.

Study procedures. After the informed consent document has been reviewed and signed, participants will be scheduled to complete a study intake assessment with the Project Manager or a Research Assistant. Once eligibility is determined, participants will be randomized to study condition. To allow an estimate of effect size for a larger trial, we will use a “treatment as usual” control group, and participants will be randomly assigned to a group. The treatment as usual group will consist of a referral to counselling services at PMMH, with the option of participating in the group sessions later (i.e. the next time the group is offered). Participants who will be postpartum by that time will be offered the option of attending a series of open problem-solving groups. With permission of the participants, we will send a referral letter documenting that criteria for depression have been met to a public health facility of the participants’ choosing to facilitate treatment for all participants who complete the baseline evaluation. Participants who do not wish to have a letter of this nature sent to a facility will be provided with a letter directly, if desired. We will also refer ALL participants who meet study inclusion criteria (or, those who do not meet criteria but could benefit from, or wish to be referred) to counselling services at PMMH,

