where there is a social worker, psychiatrist, and trauma specialist on site. To facilitate referral, we developed a referral letter in collaboration with staff at PMMH (included with this application) that has been used in other studies with similar populations. Acutely distressed or suicidal participants will be escorted directly to counselling services by study staff. The screening that occurs as part of this study goes beyond the standard of care for depression screening and thus, women may actually benefit from the screening process. The specific referral path is described below.

The study staff will be trained to identify participants with symptoms of depression during data collection through self-reporting or using the assessment measures. Study staff will complete a referral letter and refer the participant to the project manager/coordinator. The project manager/coordinator will then discuss the depression symptoms identified with the participant, as outlined on the referral letter. She will explain to the participant the purpose of referral to the clinic healthcare provider for assessment, counselling and further management. Each participant will be escorted by the study staff to the service point healthcare provider. The healthcare provider will assess the patient, counsel, treat or refer to the hospital Social Worker or Psychologist or Crisis Centre for further appropriate management.

The initial intervention will consist of 5 to 8, 90-minute, weekly sessions. Each session will begin with a brief “open” check-in among group members to foster relationships and social support among group members. The remaining session time will consist of teaching problem-solving skills for managing depression and adherence. While participants will be encouraged to attend group sessions at a regularly scheduled time to facilitate group cohesion, a total of three group sessions will be offered each week to facilitate group attendance.

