Baseline assessments will occur until it is deemed that enough participants are available for randomization and to run a group. For example, baseline assessments may occur until a minimum of four participants are identified (two intervention participants, and two control participants). In the event that recruitment is difficult, the investigators may run sessions with as few as two participants (one intervention participant, and one control participant). Participants will complete assessments with an interviewer (constructs described below in Table 1) at the following time points: once before the intervention begins, once after all intervention sessions are completed, and once at approximately three months postpartum. Control participants will be assessed at times mirroring that of the intervention participants.

As noted above, we will use an iterative process of intervention development. Interventions will be held in waves whereby an intervention group will be conducted, feedback collected from participants on the intervention, and another intervention group conducted. This process will be completed up to three times. In order to collect feedback from participants, the opportunity to participate in a brief qualitative interview will be offered to a random sample of intervention participants at the conclusion of each wave of intervention sessions. This qualitative interview is optional, and would be in addition to the aforementioned assessments. Approximately 3-5 participants per wave of intervention sessions will be randomly selected (a total of 10-15 interviews, maximum) to provide feedback on the intervention. If data from the qualitative interviews suggests that changes be made to the intervention (e.g., changing the number of sessions, changing the length of sessions, etc.), the investigators will propose changes and submit them to the ethics committee for consideration prior to starting the next wave of group sessions.

Sources of Materials: In order to maximize the integrity of the data, a racially and ethnically concordant female interviewer, fluent in both English and isiZulu, and who is different from the

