study interventionist, will complete assessments with each participant. After eligibility is determined, assessments will occur immediately pre and post intervention; a third and final assessment will occur at approximately three months postpartum (see Table 1 for constructs and measures). In addition to a self-report measure of adherence, each participant will also be provided with a Medication Event Monitoring System (MEMS) to monitor their adherence to ARVs. Data from the MEMS caps will be uploaded at the beginning of each intervention session, and at all assessment visits. Feasibility will be documented as depicted in Figure 3. Qualitative interviews will be conducted with a sub-sample of participants at the end of the group in order to describe the acceptability and perceived usefulness of the intervention. Interviews will follow a structured interview guide, with flexibility to explore probes and content that may not specifically be in the guide to begin with. Questions will be open-ended to most effectively elicit information without biasing participants' responses.

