Participants will have as much time as they require to decide if they want to participate, even if this requires re-scheduling other portions of the visit to allow the participant more time to review the informed consent document. All procedures and protocols will have been approved by the Massachusetts General Hospital (MGH) institutional review board (IRBs) and the Wits University Human Research Ethics Committee and by PMMH and local and KwaZulu-Natal provincial health authorities before the inception of any study procedures.

Data analytic plan. All analyses conducted as part of this field test intervention are meant to lay the groundwork for future work, and it is not necessarily powered to detect statistically significant changes in depression, adherence, stigma, or social support. Because this is an

exploratory study, we will first examine the outcome variables continuously. We may determine cut-off scores that are appropriate to the sample and make clinical sense, and examine dichotomous outcomes (e.g., a reduction of 30-50% in depressive symptoms and/or the percentage of the sample scoring lower than $>/= 9$ on the Edinburgh Postnatal Depression Scale (EPDS) and achieving $\geq 90\%$ adherence) when assessing the effect of the intervention. Descriptive measures (such as mean, standard deviation, median, and range) will be used to summarize continuous patient characteristics (such as age, income) and categorical patient characteristics (such as ethnicity, employment status) will be summarized using frequencies and percent's. Descriptive data on the feasibility outcomes depicted in Figure 3 will be presented. With respect to qualitative exit interviews, data will be analysed using standard qualitative methodologies described by Miles and Huberman⁴⁶. After transcripts are translated to English, they will be reviewed for errors and omissions. NVivo software (version 9) will be used to organize data and to facilitate analyses. Two investigators, one of whom will be a South African study staff member (to ensure accurate interpretation), will independently review the transcripts in order to generate an overarching thematic framework for data interpretation, in which major and minor themes are identified.

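### No masking to arm is specified for the interviewer at the two post-randomisation assessments, so the interviewer-administered outcomes are open to assessor bias

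*Combined protocol and SAP*

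**What the plan says.** All locations are in Section 3 of the combined protocol and SAP.

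- **Sources of Materials.** With data integrity as the stated aim, the interviewer is to be female, racially and ethnically concordant, "fluent in both English and isiZulu, and who is different from the" "study interventionist, will complete assessments with each participant" (one continuous sentence).
- **Study procedures.** "Participants will complete assessments with an interviewer" before the intervention, after its last session, and at about three months postpartum. Controls are assessed at matching times. The control condition is treatment as usual, so participants know their arm. Its purpose is given as "To allow an estimate of effect size for a larger trial".
- **Recruitment procedures.** The plan is to "enrol/randomize up to 40 (20 treatment and 20 control) HIV infected women".
- **Data analytic plan.** The study is exploratory and "it is not necessarily powered to detect statistically significant changes in depression, adherence, stigma, or social support".
- **Table 1.** Outcomes include the EPDS at all three time points, the MINI depression module (no follow-up schedule given), three HASI-P stigma subscales, a social support scale, self-reported adherence items with a 30-day VAS, and MEMS.

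The text does not say that the interviewer is masked, who may hold the allocation, or that women should be asked not to mention their group.

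**The concern.** Separating the interviewer from the interventionist stops the interventionist from rating her own work and may make women more candid. It does not stop a different interviewer from knowing the arm. An interviewer who knows it can, without intending to, vary how she prompts, clarifies and records answers. Most of the psychosocial outcomes are obtained in this way, and depression, stigma and social support have no objective counterpart in Table 1.

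What is at stake is the between-arm effect size that the control group was included to supply. A small pilot's imprecision shows in its confidence interval. A systematic shift from the assessor does not, and it passes into the planning of the larger trial.

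**Working it through.** **1. Is masking provided for anywhere?** Sources of Materials gives separation from the interventionist and nothing more. Study procedures, Data and safety monitoring, and Table 1 add nothing on masking. I could not see the flow chart in Figure 4, so the finding is that masking is not specified in the text.

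**2. Could the interviewer learn the arm?** Four activities belong to the intervention arm only:
- MEMS uploads at the start of each session (Sources of Materials)
- R50 paid at each session (Remuneration)
- scheduling of the weekly groups, with three sessions offered per week (Study procedures)
- optional feedback interviews with intervention women at the end of each wave, close in time to the post-intervention assessment (Study procedures)

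The plan does not say who uploads MEMS data at sessions, pays, schedules or randomises. Nothing keeps the outcome interviewer out of these tasks.

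**3. Which measurements are exposed?**

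| Measurement | Exposed to assessor bias? |
|---|---|
| Any baseline measure | Largely no: collected before randomisation |
| EPDS, stigma, social support at the two later visits | Yes |
| Self-reported and VAS adherence at the two later visits | Yes |
| MINI | Yes, if repeated after randomisation |
| MEMS adherence | Largely no: electronic record |

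**4. Could the pilot reveal such a bias?** The plan states no alpha, SD, target effect or power, so it has no figure of its own to reproduce. Take 20 per arm, full retention, independent observations and outcomes in SD units:

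- SE of the difference = √(2/20) = 0.316 SD
- 95% half-width = 1.96 × 0.316 = 0.62 SD

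A shift of a few tenths of an SD lies well inside this interval and could not be recognised from the data. For the dichotomous EPDS outcome that the Data analytic plan contemplates, one woman moved across the cut-off changes an arm's percentage by 1/20 = 5 points.

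**5. Illustration of the consequence (all effect and bias sizes assumed).** For a two-sided 5% test with 80% power, the later trial needs n per arm = 2 × (1.96 + 0.84)² / d², which is about 15.7/d². Its real power, if the true effect is 0.5 SD, is Φ(0.5 × √(n/2) − 1.96).

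| Assumed inflation (SD) | Pilot estimate d (SD) | n per arm planned | Real power at 0.5 SD |
|---|---|---|---|
| 0 | 0.5 | 63 | 80% |
| 0.1 | 0.6 | 44 | 65% |
| 0.2 | 0.7 | 33 | 53% |
| 0.3 | 0.8 | 25 | 42% |

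Nothing in the documents supports one row over another. The table shows only how an unseen shift would carry forward.

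**The case against.** **Silence is not the same as being unmasked.** This stands. A reader might infer that the interviewer knows the allocation, but no sentence says so. The supportable statement is that masking is not specified.

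**The Project Manager as a source of bias.** A reader might infer this from two statements in Study procedures: "participants will be scheduled to complete a study intake assessment with the Project Manager or a Research Assistant" and "The project manager/coordinator will then discuss the depression symptoms identified with the participant". The documents do not support it. Intake comes before randomisation, so there is no arm to know at that point. Referral applies to every woman who meets the criteria, in both arms, so it reveals nothing about allocation. Nowhere is the Project Manager said to collect post-randomisation outcomes.

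**Adherence has an objective measure.** This also stands. All participants receive MEMS, read at every assessment visit, so for adherence the concern is confined to the self-report items and the VAS.

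**The instruments are mostly fixed-response scales and staff are trained.** This has some force. Structured items leave less room for the interviewer than a diagnostic interview does, and the main reporting bias may come from the women's own expectations, which masking the interviewer would not remove. It reduces the likely size of assessor bias without removing it, because the items are still asked and recorded by a person.

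**It is a pilot, and masking may be hard to keep.** A wave may contain as few as one intervention and one control woman, all at one clinic, and questions on social support may prompt disclosure. The gain may therefore be partial. But disclaiming power answers only the question of precision, and the plan still intends to carry the effect size forward.

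**Conclusion.** The point holds in a limited form. The plan separates the interviewer from the interventionist but specifies no masking to arm. The EPDS, stigma, social support and self-reported or VAS adherence at the two post-randomisation assessments, and the MINI if repeated, are therefore open to assessor bias in an open comparison. Baseline and MEMS adherence are largely unaffected.

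The magnitude is not estimable from the documents. The 0.62 SD half-width rests on 20 women per arm, full retention and no clustering by group. The later-trial figures rest on an assumed true effect of 0.5 SD and an assumed inflation of 0.1 to 0.3 SD in favour of the intervention.

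This is a worthwhile, cheap improvement to an exploratory pilot. It does not invalidate the study, and it does not bear on the feasibility and acceptability aims.

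**What to change.** In Section 3, under Study procedures and Sources of Materials, state that:

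- the interviewer for the post-intervention and three-month postpartum assessments is masked to arm;
- she takes no part in randomisation, group scheduling, session MEMS uploads or session reimbursements, and conducts no intervention-feedback interview with a woman before that woman's outcome assessment;
- each woman is asked at the start of the interview not to say which group she was in;
- the interviewer records after each assessment whether she believes she was unmasked, and how.

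Table 1 should also say whether the MINI is repeated after randomisation. If Figure 4 already shows a masked assessor, the text need only be brought into line with it.

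**Cost.** Sample size, visits, instruments and the referral path do not change. A separate interviewer is already planned, so the cost is tighter rostering, one sentence in the interview script and one field on the form. Staff numbers are not stated, so the sponsor must confirm that the duties can be divided. Some unmasking will still occur, and participant expectation bias remains; both should be acknowledged when the effect size is reported.

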Foreseeable risks and discomforts. It is unlikely that participants will be at any risk for physical harm as a result of study participation. However, subjects may find some of the questions asked during the interviews to be emotionally upsetting. If this occurs, or if participants endorse active suicidality or exposure to intimate partner violence, they will be given the opportunity to cease study participation, and will be referred for counselling services as described above. As with any study, there is always the risk of inadvertent breach of confidentiality. This is of particular importance here because participants are infected with HIV, which may be stigmatizing. An additional discussion of how we minimize these risks is described above under "Minimization of risks".

Expected benefits. Participants in an intervention group may experience a reduction in depressive symptoms and an increase in adherence to the PMTCT cascade, including antiretroviral therapy. Study staff will refer participants to appropriate social services as needed or upon request. The data collected as part of this study may ultimately help researchers and

clinicians better care for HIV infected women and their children.

Equitable selection of participants. All women presenting for care at antenatal clinic at PMMH and meeting inclusion criteria will be invited to participate in the current study. We have budgeted time for research assistants to be physically located at the antenatal clinic to encourage and insure adequate recruitment. Men have been excluded from study participation because the aims of the study relate specifically to women. Children under the age of 18 are excluded as we are interested in studying the phenomenon of adherence to PMTCT among adult women; women under the age of 18 likely face additional and different barriers to PMTCT adherence than women 18 years or more.

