Remuneration. Refreshments will be served at all assessment and intervention visits. There are three main interviews in this study. Participants will be reimbursed R100.00 for each interview where we collect data from participants (at the beginning of the study, after the group counselling intervention / 8-10 weeks after participant first interview, approximately three months postpartum). There is also an optional qualitative interview; participants who are selected to participate and complete this interview will be reimbursed R100.00. In order to support transport costs to sessions, participants in the intervention group will also be reimbursed R50.00 at each intervention session.

Consent procedures. Two informed consent procedures will occur; the first will occur before the eligibility screening, and the second will occur before study enrolment.

A detailed pre-screening informed consent form will be signed by each participant willing to participate in the eligibility screening questions. The consent form will include information about the study procedures, and the nature of the screening questions. It will also state that participants do not have to answer any questions they do not want to answer, and that they may stop the screening at any time. Participants will be informed that they do not have to answer any question they do not want to answer, they may stop the screening at any time, and that their answers will remain anonymous and confidential.

A detailed study consent form will be signed by each participant willing to participate in the study, following the explanations of the study procedures by the research project staff.

The study consent form will include all of the study procedures, information about potential risks and benefits of participation, and information regarding who they can contact for further questions. It also will state that participation is voluntary, that participants can refuse to answer any question, that they can withdraw from the study at any time, and that study participation is in no way related to their care. Participants will also be reminded to take care when storing the consent document to avoid inadvertent disclosure of HIV status. Participants will also be informed that depression treatment is available via a referral for mental health treatment at PMMH, and thus they do not need to participate in the study in order to receive depression treatment.

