Data and safety monitoring. Data collection occurs in the form of a series of quantitative assessment interviews. The principal investigator ([name]) and her primary mentor ([name]) will work closely with the South African site PI ([name]), to oversee all data management and analysis issues. The proposed study team has extensive experience collecting data on reproductive health among women in Durban, South Africa, and a quality management plan will be developed to specify daily quality control and monthly quality assurance measures. The research assistant will review all assessments prior to the end of all interviews to minimize missing data. Data will be entered in an on-going fashion (into REDCap data management system), and will be analysed using the Statistical Package for the Social Sciences (SPSS), version 18, and QSR NVivo qualitative software, version 9, after being thoroughly checked and cleaned as appropriate. Data files will be sent to [name] from the site using secure (password protected) file transfer. The MGH IRBs will review the data-monitoring plan along with the full study protocol at least annually.

Data will be obtained from participants recruited specifically for this protocol and will include sociodemographic information (e.g., age, level in school, race and ethnicity, etc.), depression, stigma, social capital utilization, and adherence to PMTCT (see Table 1). A research assistant will collect data from the participants' record on CD4 cell count, viral load, and antiretroviral regimen during the last trimester of pregnancy and immediately postpartum, the stage of HIV as determined by World Health Organization's staging criteria, and the gestational age, date of birth, and weight of each participant's infant at birth. No other information will be abstracted from the medical record. Only trained study staff will have access to these data. Participants' data will be identified by an ID number only, and a link between names and ID numbers will be kept separately under lock and key.

The data files from the interviews will be sent by a secure file transfer system between South Africa and Boston without names and other personal identifiers. These files will be sent with a password lock known only to the key study staff. These files without any personal identifiers will be kept in Boston for 10 years, and then destroyed. Study results will be reported only in summary form so that no individual participant can be identified.

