Adverse events reporting. As a result of participation in the interview, study staff may become aware of an adverse event, including participant distress or disclosure of current or past physical or sexual abuse. Study staff will be trained to make appropriate referrals for clinical or

psychological care in consultation with the PIs and/or antenatal clinic staff and in accordance with South African law regarding the reporting of sexual or physical abuse. Adverse events will be reported according to the local South African ethics committee procedures and these will be discussed on calls between the overall PI ([name]) and the site PI ([name]).

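### Women are told before screening that their answers stay anonymous, which the protocol's own screening and referral procedures contradict; the described assurance also states no limits to confidentiality

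*Combined protocol and SAP*

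**What the plan says.** All places are in section 3 (Research Strategy) of the combined protocol and SAP.

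- **Consent procedures.** There are two consents, one before screening and one before enrolment. At the first, women are told that "they may stop the screening at any time, and that their answers will remain anonymous and confidential". The same text requires a signature: "A detailed pre-screening informed consent form will be signed by each participant willing to participate in the eligibility screening questions".
- **Recruitment procedures.** Again, "written signed consent to screening will be obtained". Then: "The research assistant will use an eligibility screening script to track all screened potential participants". The data feed study reports, and "Review of the inclusion/exclusion checklists will be part of regular supervisory meetings between the local site PI, project manager and the research assistant".
- **Inclusion and exclusion criteria.** The script includes the PHQ-2. Answers determine whether a woman is offered study consent and the baseline assessment. Women with active or untreated major mental illness, including active suicidality, are excluded and referred. Acutely distressed or suicidal women are escorted to on-site services at once.
- **Minimization of risks.** Distress or suicidality found in any study procedure is referred to the site investigator and project manager. Distressed or seemingly depressed women receive a referral letter and are passed on through the antenatal clinic's in-charge.
- **Foreseeable risks and discomforts.** "As with any study, there is always the risk of inadvertent breach of confidentiality". The text then says this matters particularly here because HIV may carry stigma, and points back to Minimization of risks.
- **Adverse events reporting.** Abuse disclosed in the interview is handled "in accordance with South African law regarding the reporting of sexual or physical abuse".

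**The concern.** Anonymous and confidential are different promises. Anonymous means that nobody can connect the answer to the person. Confidential means that those who can connect them restrict who else learns of it, subject to stated exceptions. The screening assurance makes both promises, and its description gives no exceptions.

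A woman may therefore report depressive symptoms or suicidal thoughts in the belief that they cannot be tied to her, and then be referred or escorted because of them. The referral may well be in her interest, but she should know of it before she answers. The protocol itself names fear of disclosure as a barrier to care in this population (Conceptual framework), so a promise that turns out untrue could also cost trust and retention. That last effect is plausible but is not quantified anywhere in the document.

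**Working it through.** No arithmetic underlies the main point. The check sets the promise beside each procedure that touches screening answers.

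1. **Is the respondent identified?** Yes. She is approached in the clinic queue, speaks with the research assistant and signs a consent form before answering (Recruitment procedures; Consent procedures).
2. **Are the answers tied to her when they are used?** Yes. The same woman is invited on, excluded or referred because of what she said (Inclusion and exclusion criteria). Staff cannot refer or escort a respondent they cannot identify. This step carries the conclusion. The signature and the tracking script alone would not, since the protocol does not say whether tracking is by name or by code.
3. **Can information leave the person who heard it?** Yes. The distress and suicidality pathway covers any study procedure, so it includes screening. It involves the site investigator and the project manager, and the referral route described next runs through the clinic's in-charge (Minimization of risks). Eligibility checklists are also reviewed in supervision (Recruitment procedures).
4. **Is she told of these limits before screening?** Not in the protocol's description. It covers study procedures, the nature of the questions, and the right to skip questions or stop, followed by the unqualified assurance.
5. **Does the second consent repair this?** Not for everyone. It comes after screening, and a woman excluded at screening may never reach it.

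**Reach.** The wording applies to every woman screened. That number is not given, but the up to 40 randomised women are only a subset of it.

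**Group sessions (secondary).** Every member must be HIV positive, attend the same clinic and live in Umlazi (Inclusion and exclusion criteria). Attendance can therefore reveal HIV status to the other members. The risk text names inadvertent breach, and the measures it points to concern staff and data: training, ID numbers, staff agreements and locked storage. Neither section mentions other group members. Exposure varies:

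- Individual session, or a wave with a single intervention participant: 0 peers.
- Group of 2: 2 − 1 = 1 peer.
- Group of about 10: 10 − 1 = about 9 peers.

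Three sessions are offered each week, so the peers a woman meets may also change. Up to 20 women are assigned to the intervention, and controls may join a group later.

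**The case against.** The strongest reply is that the protocol protects confidentiality well and that this is one loosely chosen word. Data are coded, locked and restricted to trained staff, and files leave the site without names. The letter to an outside facility is sent only with the woman's permission, after baseline, and can be handed to her instead (Study procedures). The pre-screening form is described as detailed and may state limits. The full form is not in the public document, so this cannot be checked.

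Much of this stands, and it rules out several stronger readings that a reader might infer:

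- *That the study breaks confidentiality.* Not shown. Referral into care is a limit to be disclosed, not evidence of a breach.
- *That screening answers fall under legal reporting of abuse.* The reporting text is tied to the interview, and nothing says that the screening script asks about abuse. The exception matters at screening only to the extent that abuse may be disclosed there.
- *That screening answers sit in the name-to-ID file.* The protocol says that "a link between names and ID numbers will be kept separately under lock and key", but of participants' data. It does not say that screening answers are held this way.
- *That the protocol treats the confidentiality risk as merely routine.* The next sentence singles out HIV and stigma, and women are reminded to store the consent document with care.
- *That the groups have no confidentiality rule.* The intervention manual is an appendix that is not in the public document, so absence cannot be asserted.

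None of this rescues the word anonymous. The permission clause does not cover the escort, or the referral to the site investigator, project manager and clinic in-charge, for which no permission step is described.

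**Conclusion.** The point holds in a limited form. The promise of anonymity is untrue as written, because the protocol's own procedures identify each screened woman and act on her answers. As described, the screening assurance also omits the limits to confidentiality that the protocol applies elsewhere. This is a participant-protection fault in the consent text and should be corrected. It has no effect on sample size, power or analysis, and no numerical effect on outcomes is claimed.

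The secondary point is smaller. The risk sections name neither disclosure to fellow group members nor a safeguard against it. Whether the manual does is an open question for the sponsor.

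Both conclusions rest on the protocol's description of the consent process. If the pre-screening form already states the exceptions, the omission shrinks to a gap in the protocol's summary, but the conflict over anonymity in the protocol text remains.

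**What to change.** 1. In Consent procedures and in the pre-screening consent form, drop the promise of anonymity and say that answers are confidential.
2. In the same place, state before screening the exceptions that the protocol already applies: referral or escort for distress or suicidality and, so far as abuse may be disclosed at that stage, reporting under South African law as in Adverse events reporting. No clinical pathway needs to change.
3. In Foreseeable risks and discomforts, name disclosure of HIV status to other group members as a risk of group sessions.
4. Confirm that the intervention manual contains a group confidentiality undertaking. If it does not, add one at the first session.

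The cost is an amendment to protocol and consent wording, plus a few minutes at session one if an undertaking has to be added. A few women may decline screening once told the limits, which is an informed choice.
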